7. Inability to confirm abstinence from cannabis or CBD or THC-containing products Ascertainment: urinalysis at intake and at weeks 2 and 6 and patient report.

8. Women who are breastfeeding, pregnant, or at risk of becoming pregnant during the course of the study. Ascertainment: a) current pregnancy will be assessed by self-report and by a pregnancy test given to all women post-menarche and pre-menopausal onsite or for remote patients, at their initial testing visit); b) breastfeeding will be assessed by self-report; and c) if pregnancy is a risk, patients will be excluded if they plan to become pregnant during the course of this study or indicate an unwillingness to use an effective birth control method – these include double barrier methods (condom plus spermicide, or diaphragm plus spermicide), birth control, and abstinence.

9. Patients who are taking or plan to take warfarin, metronidazole, paraldehyde, phenytoin, theophylline, oral anticoagulants, or isoniazid (Patient report)

10. A concurrent or recent illness that may better account for current fatigue (Review of history)

11. Unwillingness to not take any new non-emergency medications during the course of this study without first reviewing with the study research physician (Patient Report)

12. History of rubber-contact dermatitis or allergy to disulfiram or thiuram derivatives (patient report)

13. Prior history of serious adverse reaction to disulfiram (Patient Report)

14. Cognitive Impairment for patients over 60. Patient's with scores of less than 24 on the Mini-Mental Status Exam will not be eligible for this study.

15. Suicidal acts in the last 6 months (Screening Form) or current suicidal thoughts with intent or plan (assessed at intake by the study clinician and by the MINI). History of bipolar disorder (MINI).

16. Remote participants only: Unwillingness to provide a local physician who will provide secondary monitoring and collaborate to complete physical exams as part of study (patient report, screening form)

17. Remote **and hybrid** participants: Unwillingness to attend all required safety testing at his/her local Quest testing center (patient report, screening form).

Inclusion/Exclusion Criteria #2

Name the subject group/sub sample Highly Probable Create or insert table to describe the inclusion criteria and methods to ascertain them 1. Meets criteria for any one of the 4 follow categories of Highly Probable past Lyme Disease:

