On the intake day of the study, the nature of the research evaluation protocol, including potential risks and benefits, will be explained verbally to all potential subjects by an experienced member of the study team who is knowledgeable about all aspects of the evaluation process. Participants will be asked to also read the study Consent and HIPPA Forms. The person obtaining consent will answer any questions the subject may have. Once he/she feels confident the subject understands the evaluation description, he/she will obtain informed consent from the subject by having him/her sign the consent form. Participants will be verbally reminded of the key points of the consent form and procedures of the evaluation at the beginning of each study visit.

The study clinician will have a detailed and frank discussion about participants' cannabis and alcohol use and the risks of using these substances while taking disulfiram. The study clinician will also inquire if the patient is either vegan or lactose intolerant. If the patient reports being either of the two, then the pharmacy will be informed about the specific dietary restriction immediately following the intake visit. Documentation of this discussion and participants plan for not using these substances will be made in the consent procedure note.

Physical examination, sensory testing and collection of biological samples

A medical history and physical examination will be conducted, including sensory testing (pain, sound, vibration, sweat gland function). The Neuropathy Total Symptom Scale- 6 and the Total Neuropathy Scale will be administered by the clinician during the neurologic assessment at intake and at week 8. EKG will be conducted by one of the study RAs and read by one of the study clinicians in order to confirm the participants' inclusion/exclusion criteria during the intake visit.

The following tests will be performed during the study:

• CBC, Chemistry Screen, TFT (Tests performed at Nathan Klein Clinic- CBC and Chem screen with LFTS will be conducted at intake, baseline, wk 1 (post tx), 2, 4, 6, 8, and 10, study while TFTs will be done only at intake, Tox Screen will be done at Intake and Wks 2 and 6)

• Lyme, Babesia Microti (Tests performed only at intake)

• Lyme Urine Proteome Test (Test performed by the Center for Applied Proteomics and Molecular Medicine at George Mason University.- done at intake and Week 10)

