• Fecal matter samples collected at intake, week 4, week 8 and at week 10 will be sent to our collaborator [name] at Northeastern University

• All females who are post-menarche and pre-menopausal will be required to take a urine pregnancy test at the time of the intake (Test performed at NYSPI)

• EKG (Test performed at NYSPI- done at intake)

• Storage for biorepository for analysis at the end of the study. This will include Blood (serum, plasma, whole blood) and urine collected at baseline, week 4, week 8, and week 10). (More information is provided in the blood and other biological samples subsection)

While some of these samples will be sent to known collaborators, others will be stored in anticipation of future collaborations. The known collaborators for stored samples include samples to: a) the Center for Applied Proteomics at George Mason University; b) [name] at Columbia for inflammatory and immune markers; c) [name] at Columbia for coinfection markers; and d) Drs. [name] (University of Missouri) and [name] at (UCSD) for lipidomic markers.

REMOTE INTAKE AND STUDY VISITS- (please see attached study overview visit checklist document for visit breakdown)

Informed Consent and HIPPA Forms

On the day of the intake visit, the nature of the research evaluation protocol, including potential risks and benefits, will be explained verbally via a secure telehealth platform to all potential subjects by an experienced member of the study team who is knowledgeable about all aspects of the evaluation process. Participants will be asked to also read the study Consent and HIPPA Forms. The person obtaining consent will answer any questions the subject may have. Once he/she feels confident the subject understands the evaluation description, he/she will obtain informed consent from the subject by having him/her sign the consent form and scanning and returning them via a secure platform. Participants will be verbally reminded of the key points of the consent form and procedures of the evaluation at the beginning of each study visit.

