The study clinician will have a detailed and frank discussion about participants' cannabis and alcohol use and the risks of using these substances while taking disulfiram. The study clinician will also inquire if the patient is either vegan or lactose intolerant. If the patient reports being either of the two, then the pharmacy will be informed about the specific dietary restriction immediately following the intake visit. Documentation of this discussion and participants plan for not using these substances will be made in the consent procedure note.

Physical examination

A medical history will be conducted via telehealth by a study clinician and a physical examination will be conducted by each participant's local physician. The Neuropathy Total Symptom Scale- 6 and the Total Neuropathy Scale will be administered by the local clinician during the neurologic assessment at intake and at week 8. The results of these assessments and any visit notes will be securely faxed from the local physician's office to the study clinician.

Remote participants will be required to visit their local Quest Diagnostic testing site for the following tests that will be performed during the study:

• CBC, Chemistry Screen, TFT (Tests performed at Quest Diagnostic- CBC and Chem screen with LFTS will be conducted at intake, Weeks **2**, 4, 6, and 10, study while TFTs will be done only at intake, Tox Screen will be done at Intake and Week 6)

• Lyme, Babesia Microti (Tests performed only at intake)

• Lyme Urine Proteome Test (Test performed by the Center for Applied Proteomics and Molecular Medicine at George Mason University.- samples collected at home and sent to collaborating lab at intake and Week 10)

• Fecal matter samples collected at home at intake, week 4, week 8 and at week 10 will be sent to our collaborator [name] at Northeastern University

• All females who are post-menarche and pre-menopausal will be required to take a urine pregnancy test at the time of the intake (Test performed at Quest Diagnostic)

The results of these laboratory tests will be accessible to the study clinicians via a HIPPA compliant, secure EHR portal provided by Quest Diagnostics.

HYBRID INTAKE, BASELINE, AND STUDY VISITS- (please see attached study overview visit checklist document for visit breakdown)

Informed Consent and HIPPA Forms

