• Fecal matter samples collected at home at intake, week 4, week 8 and at week 10 will be sent to our collaborator [name] at Northeastern University

• All females who are post-menarche and pre-menopausal will be required to take a urine pregnancy test at the time of the intake (Test performed at Quest Diagnostic)

• Storage for biorepository for analysis at the end of the study. This will include Blood (serum, plasma, whole blood) and urine collected at baseline and week 10). (More information is provided in the blood and other biological samples subsection)

The results of laboratory tests done through Quest will be accessible to the study clinicians via a HIPPA compliant, secure EHR portal provided by Quest Diagnostics.

While some of these samples will be sent to known collaborators, others will be stored in anticipation of future collaborations. The known collaborators for stored samples include samples to: a) the Center for Applied Proteomics at George Mason University; b) [name] at Columbia for inflammatory and immune markers; c) [name] at Columbia for coinfection markers; and d) Drs. [name] (University of Missouri) and [name] at (UCSD) for lipidomic markers.

All Participants (Remote, Hybrid and In-Person) will also complete the following as part of study visits:

Medical history and psychiatric diagnostic Interview MINI

At intake, all subjects will undergo structured diagnostic interviews in-person or via telehealth, which include questions about their current and psychiatric history using MINI. A medical history will be obtained at intake using the Self-Administered Comorbidity Questionnaire (SCQ) and by the study clinician during the clinician interview.

Self-report questionnaires

Participants will have in-person or telehealth assessments at baseline and at weeks 1, 2, 4, 6, 8, 10. Participants will complete self-report questionnaires every 2 weeks at each assessment throughout the study and at Week 14.

These self-report questionnaires and research data will be collected electronically via REDCap (Research Electronic Data Capture), hosted by New York State Psychiatric Institute. REDCap is a secure web application for building and managing online surveys and databases that complies with HIPAA requirements for a secure database.

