• A patient will be discontinued from treatment early if he/she shows signs of liver toxicity on laboratory tests; an abnormal finding (e.g., Moderate or Severe ALT elevation > 2x ULN or AlkPhos > 1.5x ULN or Bili > 1.5x ULN) will lead to a discontinuation of the treatment, repeat of the lab test with close monitoring of the patient, and a referral for the patient to see their internist for further liver monitoring. If patients experience any mild ALT elevation or Alk Phos elevation (e.g., ALT >ULN but <2x ULN or ALK Phos >ULN <1.5x ULN), then the study clinician will keep their disulfiram dose the same and repeat testing in 2 weeks as long as their TB remains <1.5 ULN. Patients will be advised to immediately notify their study clinician of any early symptoms of hepatitis, such as fatigue, weakness, malaise, anorexia, nausea, vomiting, jaundice or dark urine; this will lead to a medical evaluation to rule out liver involvement.

• Patients will also be discontinued from the treatment component of the study early if they experience any new onset adverse neurological reactions thought to be due to the study treatment and which persists for at least 1 week (e.g., polyneuritis, peripheral neuropathy).

Clinically, early discontinuation from treatment will occur if:

a. a patient's self-report on the CGI Global Change scale indicates a score of "very much worse" for 2 consecutive weeks or "much worse" for 4 consecutive weeks.

b. a patient's score on the BDI item 9 suicide item is 2 or higher for 2 consecutive assessments. A BDI item 9 score of 2 or 3 will lead to an evaluation by a psychiatrist and closer monitoring which will include a reassessment one week later. If the worsening suicidal ideation continues, the patient will be withdrawn from the study and appropriate clinical care will be arranged.

Blood and other Biological Samples

Please create or insert a table describing the proposed collection of blood or other biological specimens

IN-PERSON PARTICIPANT SPECIMEN COLLECTION:

The following will be drawn or collected for in-person participants:

Intake

- CBC, Chemistry Screen, TFT (Tests performed at NKI)
- 1. CBC- 1 4cc EDTA
- 2. TFTs and Chemistry Screen- 2, 8cc Red Top
- 3. Tox Screen and Pregnancy Test- 50 cc Urine

Lyme and Babesia test (Tests performed at MDL) 1. 2, 8.5cc Serum Tube

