Stool collection kit is given to patient at intake visit. Patient is to collect stool sample at home and send to [name] lab at Northeastern- kits prior to the Baseline visit.

Baseline/Wk0

Lyme Proteome Test (Test performed at George Mason University) 1. 80cc Urine Sample

Storage for Biorepository-

- 1. 2, 8 cc Red top Serum Tube- stored in .25cc aliquots
- 2. 1, 8cc EDTA Plasma-tube stored in .5cc aliquots
- 3. 1, 4cc EDTA Whole Blood stored in .5cc aliquots

CBC, Chemistry Screen, LFT (Tests performed at NKI)1. CBC- 1 4cc EDTA2. TFTs and Chemistry Screen- 2, 8cc Red Top

Weeks 1, 2, 4, 6, 8 CBC and Chem screen (including LFTs). Urine Tox Screen at Wks 2 and Wk 6

Week 4 & 8

Storage for Biorepository-

- 1. 1, Serum from one 8cc Red Top Tube
- 2. 1, Plasma from one 6cc EDTA Plasma Tube
- 3. 50cc Urine Sample

Stool sample (collected at home and sent to [name] lab at Northeastern)

Week 10

- CBC and Chem screen (including LFTs)
- 1. CBC-1 4cc EDTA
- 2. TFTs and Chemistry Screen- 2 8cc Red Top

Lyme Proteome Test (Test performed at George Mason University) 1. 80cc Urine Sample

Storage for Biorepository-

- 1. 2, 8 cc Red Top Serum Tube- stored in .25cc aliquots
- 2. 1, 8cc EDTA Plasma-tube stored in .5cc aliquots
- 3. 1, 4cc EDTA Whole Blood stored in .5cc aliquots

Stool sample (collected at home and sent to [name] lab at Northeastern)

REMOTE PARTICIPANT SPECIMEN COLLECTION:

The following will be drawn or collected for remote participants:

Intake

CBC, Chemistry Screen, TFT (Tests performed at Quest Diagnostics)

- 1. CBC-1 4cc EDTA
- 2. TFTs and Chemistry Screen- 2, 8cc Red Top

3. Tox Screen and Pregnancy Test- 50 cc Urine

Lyme and Babesia test (Tests performed at MDL) 1. 2, 8.5cc Serum Tube

Stool collection kit is mailed to patient after intake telehealth visit. Patient is to collect stool sample at home and send to [name] lab at Northeastern prior to the Baseline visit.

Baseline/Wk0

Lyme Proteome Test (Test performed at George Mason University) 1. 80cc Urine Sample (Participants will be mailed a urine collection kit. Urine sample is to be collected at home and sent to George Mason University collaborators)

Weeks 2, 4, & 6

CBC and Chem screen (including LFTs). Urine Tox Screen at Wk 6 only (Tests performed at Quest Diagnostics)

Week 4 & 8 Stool sample (collected at home and sent to [name] lab at Northeastern)

Week 10

CBC and Chem screen (including LFTs) - (Tests performed at Quest Diagnostics)

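### Remote and hybrid schedules omit the week 2 cannabis urine screen that exclusion 7 sets for everyone, so in those modes the 4-week arm has none during active disulfiram

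*Combined protocol and SAP*

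**What the plan says.** **Cannabis.** Item 7 of the exclusion criteria, worded alike for the main group and the Highly Probable group, gives the method and timing: "Ascertainment: urinalysis at intake and at weeks 2 and 6 and patient report". It makes no distinction by participation mode.

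Study Procedures then sets a schedule for each mode. In person: "Tox Screen will be done at Intake and Wks 2 and 6". Remote and hybrid, in the same words: "Tox Screen will be done at Intake and Week 6". The specimen lists under Blood and other Biological Samples repeat the split. In-person participants are screened at weeks 2 and 6; for both other modes the entry for weeks 2, 4 and 6 reads "Urine Tox Screen at Wk 6 only (Tests performed at Quest Diagnostics".

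**Treatment.** Under Treatment Phase, both arms take disulfiram for the first 4 weeks. The short arm then takes placebo in weeks 5 to 8, while the long arm stays on disulfiram.

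**Pregnancy.** In-person women who are post-menarche and pre-menopausal "will be required to take a urine pregnancy test at the time of the intake (Test performed at NYSPI". For remote and hybrid women the entry is "urine pregnancy test at the time of the intake (Test performed at Quest Diagnostic". The specimen lists place "Tox Screen and Pregnancy Test- 50 cc Urine" under Intake. Exclusion 8 asks for a test onsite "or for remote patients, at their initial testing visit". The first dose is taken at a separate baseline visit.

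**The concern.** A site cannot follow both exclusion 7 and the remote or hybrid schedule. The authors did mark differences by mode elsewhere in the same list (items 1a, 16 and 17), so the absence of any such mark on item 7 reads as a rule for everyone.

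The protocol's own risk section says that cannabis combined with disulfiram raises the risk of psychosis. Week 2 is also the last scheduled in-person screen before the dose rises above 250 mg a day. Remote and hybrid participants go through that escalation with no urine check since intake.

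Safety is primary aim 1. Undetected cannabis use could produce psychiatric events that are then put down to disulfiram, and the chance of detecting use would differ by mode.

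**Working it through.** The plan states no figure here, so the check compares schedules and counts screens.

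**Step 1. Scheduled urine tox screens** (exclusion 7, the three test lists in Study Procedures, and the three specimen lists):

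| Source | Intake | Week 2 | Week 6 | Total |
|---|---|---|---|---|
| Exclusion 7, both groups | yes | yes | yes | 3 |
| In person | yes | yes | yes | 3 |
| Remote | yes | no | yes | 2 |
| Hybrid | yes | no | yes | 2 |

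Shortfall against exclusion 7 for remote and hybrid: 3 − 2 = 1. Each of these two schedules is stated twice in the protocol, and the two statements agree.

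**Step 2. Screens during active dosing** (Treatment Phase):

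- Active dosing in the 4-week arm: day 0 to 4 × 7 = day 28.
- Active dosing in the 8-week arm: day 0 to 8 × 7 = day 56.
- Week 2 screen: 2 × 7 = day 14. Week 6 screen: 6 × 7 = day 42.
- Day 42 falls 42 − 28 = 14 days after active dosing ends in the 4-week arm, and inside active dosing in the 8-week arm.

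| Arm | In person | Remote or hybrid |
|---|---|---|
| 4-week | 1 (day 14) | 0 |
| 8-week | 2 (days 14 and 42) | 1 (day 42) |

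**Step 3. Other contact in the first 4 weeks.** All modes have assessments at weeks 1, 2 and 4 and a clinician call at the end of week 3: 3 + 1 = 4 contacts, one a week. The call is stated to ask about alcohol and cannabis. The text does not say that the assessments do, although consent points are repeated at each visit. None of this contact is a urine test.

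**Step 4. Would a week 2 screen add a visit?** No. The remote and hybrid lists already place a blood count and chemistry at Quest in week 2, and results already reach the study clinicians through the Quest portal.

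**Step 5. Pregnancy tests listed, each mode:** 1 at intake, 0 at Baseline/Wk0, 0 later. The intake-to-baseline interval is not stated. The activity monitor is worn for 2 weeks before randomization, so the gap would be about 2 weeks or more if the monitor is issued at intake. That condition is an assumption.

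**The case against.** The strongest reply is that the omission was deliberate. The week-6-only entry is explicit and appears for both modes, and the protocol says that laboratory and in-person assessments were cut to limit COVID-19 travel risk. On that view exclusion 7 was simply not updated, and qualifying it by mode would remove the conflict. This is possible, and it would cure the inconsistency. It would not put a urine screen into the active phase of the 4-week arm. The travel reason also does not explain the cut, because the week 2 trip to Quest takes place anyway.

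A second reply is that remote and hybrid participants are watched closely. That is right as far as it goes. A reader might infer from the zero in the table that they are unmonitored on active drug; they have weekly contact, a documented discussion of cannabis and alcohol, and side-effect monitoring at visits and calls. What remains is narrower: for cannabis these safeguards rest on self-report, and exclusion 7 asks for urinalysis and patient report together.

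A third reply is that the early-discontinuation criteria give no rule for a positive tox screen, so an added screen would have no defined consequence. This stands, and the fix has to supply one.

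On pregnancy, a reader might infer that women are dosed without any prior test, or that the schedule breaks exclusion 8. The documents support neither. Intake precedes the baseline visit in every mode, and exclusion 8 is met as written. It also excludes women who plan pregnancy or will not use effective contraception, and the protocol's risk list names no fetal risk. A missing repeat test is therefore an optional improvement. The visit checklists, named as attachments but not supplied, may already contain one.

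**Conclusion.** The cannabis point holds. The remote and hybrid schedules fall one urine screen short of exclusion 7. During active disulfiram this leaves 0 screens against 1 in person in the 4-week arm, and 1 against 2 in the 8-week arm. The conflict lies within the protocol text, so the unseen checklists cannot remove it.

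The counts assume nominal visit days and treat active as the period of active dosing. They make no allowance for any drug effect that lasts after the final dose.

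The pregnancy point is secondary and optional.

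The practical reach is limited. Enrollment was stopped in 2021 and the study was terminated in 2022 with 11 participants. The documents do not say how many of these were remote or hybrid, so the number affected cannot be given. Neither point alters an efficacy endpoint or its analysis. The value is for the plan as written and for the larger trial it is meant to inform.

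**What to change.** 1. Add a urine tox screen at week 2 to the remote and hybrid test lists and specimen lists, taken at the Quest visit already scheduled and read through the existing portal. All three modes then match exclusion 7.
2. State in the early-discontinuation section, for all modes, that a positive cannabis screen leads to clinician review and holding of study drug.
3. Optional: unless the visit checklists already include it, add a urine pregnancy strip at Baseline/Wk0 for post-menarche, pre-menopausal women, with a negative result needed before the first dose. In-person and hybrid women would do it on site. Remote women would use a mailed strip, read on camera at the supervised baseline telehealth visit.

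Item 1 costs one extra urine test per remote or hybrid participant, item 2 a short text change, and item 3 one strip per eligible woman. No visit is added. A participant may occasionally have drug held, or be delayed or excluded at baseline.
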